## **7.9 Computer Methods**

Statistical analyses will be performed using SAS® version 9.2 or later under a Windows operating system.

## **8 DATA COLLECTION, MONITORING, AND RECORD RETENTION**

For the purpose of monitoring and auditing the study, source documentation will consist of existing medical records and/or study records developed and maintained by the investigator. Any source document templates provided by the sponsor or its designee will serve as supplements to the subject's study record.

Data recorded on source documents will be transcribed onto case report forms (CRFs) provided by the sponsor or entered using electronic case report forms (eCRFs) using an Electronic Data

Capture (EDC) system provided and approved by the sponsor. Completed, original CRFs will be retrieved by the sponsor or its designee and a copy of each completed CRF will be retained at the clinical site as part of the study records.

The study will be monitored regularly by the sponsor or its designee throughout the study period. For studies of unapproved investigational products, all study records (source documents, signed informed consent forms, copies of CRFs, IRB/IEC correspondence and approval letters, and study drug management records) will be kept secured for a minimum of 2 years following the marketing of the investigational product or for 2 years after the discontinuation of the IND. The investigator will ensure that study records are not disposed of or removed from the clinical site without prior notification and approval from the sponsor or its designee.

## **9 HUMAN SUBJECTS**

### **9.1 Ethics and Regulatory Considerations**

The study will be conducted according to the ethical principles set forth in the Declaration of Helsinki, ICH-GCP, Protection of Human Subjects (21 CFR 50), Institutional Review Boards (21 CFR 56), Obligations of Clinical Investigators (21 CFR 312), and local regulatory requirements.

The protocol and informed consent form will be reviewed and approved by the IRB or IEC of each participating clinical site prior to any protocol-specified procedures being conducted. The investigator will inform the IRB/IEC as to the progress of the study on a regular basis, or at minimum, once a year. The sponsor will also have an independent IRB review and approval of the protocol and informed consent form and will keep the IRB informed of the progress of the study.

Written informed consent will be obtained from each subject prior to any protocol-specified procedures being conducted.

To maintain confidentiality, subject identification numbers will be used to identify the subject's laboratory specimens, source documents, CRF, study reports, etc. All study records will be maintained in a secured location. Clinical information will not be released without written permission from the subject except as necessary for monitoring or auditing of the study by the sponsor or its designee or applicable regulatory authorities.

After the study has been unblinded, the subject should be informed which treatment (Study Drug) the subject received.

## **9.2 Institutional Review Board or Independent Ethics Committee**

All the documents the IRB/IEC may need to fulfill its responsibilities, such as the protocol, protocol amendments, information concerning subject recruitment, payment or compensation procedures, etc., will be submitted to the IRB/IEC by the investigator. The IRB's/IEC's written, unconditional approval of the study protocol and the informed consent form will be in the possession of the investigator/clinical site staff prior to the conduct of any protocol-specified procedures.

Modifications to the protocol may not be implemented without prior written IRB/IEC approval except when necessary to eliminate immediate hazards to the subjects or when the modification involves only logistical or administrative aspects of the study. Such logistical or administrative modifications will be submitted to the IRB/IEC in writing by the investigator, and a copy of the correspondence to verify the submission will be maintained.

The investigator must inform the IRB/IEC of modifications to the informed consent form or any other documents previously submitted for review/approval, of any new information that may adversely affect the safety of the subjects or the conduct of the study, provide an annual update and/or request for re-approval, and advise the IRB/IEC when the study has been completed.

Any documents or forms to be provided to the subject (e.g., information cards, form letters from the investigator), and all forms of study advertising (flyers, brochures, print advertisements, radio or television scripts, etc.) must be approved by the sponsor or its designee prior to the clinical site submitting them to the IRB/IEC. Approval from the IRB/IEC must be obtained prior to providing the documents or forms to the subject.

## **9.3 Informed Consent**

The principles of informed consent in the current edition of the Declaration of Helsinki and ICH-GCP/21 CFR 50.25 should be implemented prior to any protocol-specified procedures being conducted. Informed consent will be documented in writing on a consent form approved by the IRB/IEC.

All relevant information should be provided in both oral and written form in a way that is understandable to the subject. Ample time and opportunity must be given for the subject to inquire about details of the study. The written consent document will embody the elements of informed consent as described in the Declaration of Helsinki and will also comply with local regulations.

The investigator or the investigator's qualified designee will explain the nature of the study and inform the subject that participation is voluntary and that the subject can leave the study at any time, without penalty or loss of benefits to which they are otherwise entitled. The subject must be informed about the study's purpose including why the subject was selected to participate, study goals, expected benefits and risks, potential risks, and that some potential risks are unforeseeable. The subject must be provided with a description of the procedures and the

estimated duration of time required for participation in the study, as well as alternative interventions or courses of treatment, if applicable.

The subject must receive an explanation as to whether any compensation and any medical treatments are available if injury occurs and, if so, what they are, where further information may be obtained, and who to contact in the event of a study-related injury. The subject must be told who to contact for answers to any questions related to the study. The extent of the confidentiality of subject records must be defined and the subject must be informed that applicable data protection legislation applies.

The subject must be informed that the monitor(s), auditor(s), IRB/IEC members, and the applicable regulatory authorities will be granted direct access to the subject's original study medical records for verification of protocol-specified procedures and/or data, without violating the confidentiality of the subject to the extent permitted by the applicable laws and regulations. The subject must be informed that his/her signature on the informed consent form indicates that he/she has decided to participate in the study, having read and discussed the information presented.

Modifications made by the investigator to an informed consent form template provided to the investigator by the sponsor or its designee will be reviewed and approved by the sponsor or its designee prior to being submitted to the IRB/IEC.

The original, signed informed consent form for each subject will be maintained by the investigator as part of the subject's study records. A copy of the signed informed consent form will be provided to each subject.

## **10 STUDY COMPLETION**

At the discretion of the sponsor, all materials and supplies provided to the investigator will be returned or disposed of in compliance with local regulatory requirements upon authorization from the sponsor, upon study completion. The investigator or designated clinical site staff will notify the IRB/IEC when the study has been completed.

## **11 PUBLICATIONS**

The final study report will be made available to the principal investigator for purposes of publications. The principal investigator and study staff must send all manuscripts, abstracts, and presentations using data from this study to the sponsor for review prior to their submission. The sponsor reserves the right to delete any part or parts of such materials deemed to be confidential or proprietary.

## 12 CHANGES IN THE PROTOCOL

The protocol may not be modified without written approval from the sponsor. All changes to the protocol must be submitted to the IRB/IEC and must be approved by the IRB/IEC prior to their implementation.

### 12.1 Changes to Version 2.0 from Version 1.0.

Minor typographical, grammatical or administrative changes are not listed.

Version 1.0 Chapter	Version 2.0 Chapter	Version 2.0 change	Page
1.1 Background	1.1 Background	Discussion of the mortality of rabies vaccination alone compared to combined RIG and vaccination. Discussion of the temporal evolution of rabies virus neutralizing activity.	10
1.4 Clinical Experience with SYN023	1.5 Clinical Experience with SYN023	RVNA data from SYN023-001 presented in rationale for selection of 0.3 mg/kg as dose for current protocol	15
3.1 Schedule of subject treatment and evaluation	3.1 Schedule of subject treatment and evaluation	Table 3.1-1 Additional visit added on Study Day 1 for safety, PD and PK data point	15
3.1 Schedule of subject treatment and evaluation	3.1 Schedule of subject treatment and evaluation	Table 3.1-1 Anti-SYN023 antibody data point added on Study Day 7	15
3.1 Schedule of subject treatment and evaluation	3.1 Schedule of subject treatment and evaluation	Table 3.1-1 CPK and troponin added to safety labs.	15
3.1 Schedule of subject treatment and evaluation	3.1 Schedule of subject treatment and evaluation	Table 3.1-1 Urinalysis added Study Day 1 and 3	15
3.1 Schedule of subject treatment and evaluation	3.1 Schedule of subject treatment and evaluation	Table 3.1-1 ECG added through Study Day 28	15
3.2.3 Inclusion Criteria	3.2.3 Inclusion Criteria	Pregnancy test increased to within 48 hours preceding receipt of the first dose	18
3.2.5 Screening Clinical Assessments and Laboratory Tests	3.2.5 Screening Clinical Assessments and Laboratory Tests	Wording added that eligibility is determined by screening laboratories	19
3.3 Study	3.3 Study	4 sentinel subjects (1 for each	20

Randomization	Randomization and Sentinel Subjects	regimen) will be randomized and Study Day 14 safety data reviewed before enrollment of the remainder of the trial.	
3.5 Medicinal Product and Study Drug Administration	3.5 Medicinal Product and Study Drug Administration	Interval between Study Drug and vaccination lengthened to 75 minutes	22
3.6.2 Immunology Laboratory Evaluations	3.6.2 Immunology Laboratory Evaluations	Added Day 1 data point for PK. Added Day 7 data point for anti-SYN023 antibodies	23
3.6.3 Safety Evaluations	3.6.3 Safety Evaluations	Added ECG, anaphylaxis and immune complex wording	24
3.6.3.1 Pre-Study Study Drug and Post Administration Monitoring of Subjects	3.6.3.1 Pre-Study Study Drug and Post-Study Drug Administration Clinical Monitoring of Subjects	Added wording for clinical monitoring after all medicinal products are administered	24
3.6.3.1 Pre-Study Study Drug and Post Administration Monitoring of Subjects	3.6.3.1 Pre-Study Study Drug and Post-Study Drug Administration Clinical Monitoring of Subjects	Added drugs and listed equipment for management of acute allergic reactions	24
	3.6.3.1 Pre-Study Study Drug and Post-Study Drug Administration Clinical Monitoring of Subjects	Post SYN023 administration monitoring interval increased to 240 minutes	24
	3.6.3.2 New chapter Recognition of Anaphylaxis	Added wording requiring plasma histamine, plasma tryptase and urinary N-methyl-histamine when the diagnosis of anaphylaxis is considered.	25
	3.6.3.2 New chapter Recognition of Anaphylaxis	Wording added on recognition of anaphylaxis (Sampson)	28
	3.6.3.3 New chapter Treatment of Anaphylaxis	Added chapter on treatment of anaphylaxis (Sampson)	25

	3.6.3.4 New chapter Recognition and evaluation of Immune Complex Illness	Added chapter on recognition of immune complex induced illness	26
3.6.4 Window Periods ...	3.6.4 Window Periods ...	ECG added	28
4.2 RIG(HyperRab ST®)	4.2 RIG ((HyperRab ST®)	Wording added to permit supply by the sponsor	29
5.15 Subject Temperature Monitoring.	5.15 Subject Daily Temperature	Wording added to require temperature to be taken upon awakening.	42
6.1 Safety Pausing Rules	6.1 Safety Pausing Rules	The following wording was added to the chapter; The FDA must be notified if the Study is paused for safety reasons. The FDA must be notified if the Study is then resumed. CPK was exempted from pausing rules since elevations are anticipated with IM RIG injections	42
6.2 Safety Stopping Rules		CPK was exempted from stopping rules since elevations are anticipated with IM RIG injections. FDA wording added.	42
13 References	13 References	Added Karplod Reference	54
13 References	13 References	Added Sampson Reference for Anaphylaxis	54
13 References	13 References	Added Vodopija References	54

**APPENDIX A Detailed Description of Selected Study Visits****Screening Visit (Up to 4 weeks prior to start of study medication, Day -28 to -1)**

- Obtain informed consent
- Verify eligibility by review of inclusion/exclusion criteria
- Record medical history
- Conduct physical examination (including height and weight and BMI calculation)
- Perform ECG
- Collect urine sample for:
  - $\beta$ HCG (all females)
  - Urinalysis
  - Urine Toxicology
- Collect blood samples for:
  - Hepatitis B, Hepatitis C, HIV-1,2
  - PT and PTT
  - Serum chemistry: creatinine, ALT, AST, alkaline phosphatase and others if part of panel
  - Hematology: CBC including differential and platelets
  - Serum IgA

**Baseline Visit (Study Day 0)**

- Verify eligibility by review of inclusion/exclusion criteria
- Conduct focused physical examination including weight
- Insure that results of Serum  $\beta$ HCG are negative
- Record vital signs and oximetry
- Record interval history
- Record concurrent medications
- Collect urine sample for urinalysis
- Insure that blood samples collected for:
  - Serum chemistry: total bilirubin, BUN, CPK, troponin, creatinine, ALT, AST, alkaline phosphatase, sodium, potassium, chloride, bicarbonate calcium

- 
- Hematology: CBC including differential and platelets
  - Clotting studies: PTT and prothrombin INR
  - Anti-SYN023 antibodies
  - SYN023 antibody levels
  - Rabies Virus Inhibitory Serum Activity
  - Administer Study Drug (RIG or SYN023) on Right side of body
  - Within approximately 75 minutes administer RVa or RVi on Left side of body
  - Distribute diary and thermometer and instruct subject in their use
  - Assess patient for AEs and SAEs
  - Perform vital signs & oximetry every 30 minutes during the 240 minutes of observation prior to discharge

## APPENDIX E Toxicity Table

2. *Note: From final US FDA guidance: Toxicity Grading Scale for Healthy Adult and Adolescent Subjects Enrolled in Preventive Drug Clinical Trials (September 2007); laboratory values are in conventional and SI units. The laboratory values provided in the tables serve as guidelines and are dependent upon institutional normal parameters. Institutional normal reference ranges should be provided to demonstrate that they are appropriate.*

Local Site of Infusion Symptoms	Mild (Grade 1)	Moderate (Grade 2)	Severe (Grade 3)	Very Severe (Grade 4)
Pain	Does not interfere with activity	Repeated use of non-narcotic pain reliever > 24 hours or interferes with activity	Any use of narcotic pain reliever or prevents daily activity	ER visit or hospitalization
Tenderness	Mild discomfort to touch	Discomfort with movement	Significant discomfort at rest	ER visit or hospitalization
Erythema/Redness *	2.5 - 5 cm	5.1 - 10 cm	>10 cm	Necrosis or exfoliative dermatitis
Induration/Swelling **	2.5 - 5 cm and does not interfere with activity	5.1 - 10 cm or interferes with activity	>10 cm or prevents daily activity	Necrosis

3. \* In addition to grading the local reaction at the greatest single diameter, the measurement should be recorded as a continuous variable.

4. \*\* Induration/Swelling should be evaluated and graded using the functional scale as well as the actual measurement.

Vital Signs*	Mild (Grade 1)	Moderate (Grade 2)	Severe (Grade 3)	Very Severe (Grade 4)
Fever**	38.0 – 38.4°C 100.4 – 101.1°F	38.5 - 38.9°C 101.2 - 102.0°F	39.0 - 40°C 102.1 - 104°F	>40°C >104°F
Tachycardia – beats per minute	101 – 115	116 – 130	>130	ER visit or hospitalization for arrhythmia
Bradycardia – beats per minute	50 – 54	45 – 49	<45	ER visit or hospitalization for arrhythmia
Hypertension (systolic) – mm Hg	141 – 150	151 – 155	>155	ER visit or hospitalization for malignant hypertension
Hypertension (diastolic) – mm Hg	91 – 95	96 – 100	>100	ER visit or hospitalization for malignant hypertension
Hypotension (systolic) – mm Hg	85 – 89	80 – 84	<80	ER visit or hospitalization for hypotensive shock
Respiratory rate – breaths per minute	17 – 20	21 – 25	>25	Intubation

5. \* Subject should be at rest for all vital sign measurements. \*\* Oral temperature; no recent hot or cold beverages or smoking.

Systemic (General)	Mild (Grade 1)	Moderate (Grade 2)	Severe (Grade 3)	Very Severe (Grade 4)
Nausea/vomiting	No interference with activity or 1 - 2 episodes/24 hours	Some interference with activity or >2 episodes/24 hours	Prevents daily activity, requires outpatient IV hydration	ER visit or hospitalization for hypotensive shock
Diarrhea	2 - 3 loose stools or < 400 grams/24 hours	4 - 5 stools or 400 - 800 grams/24 hours	6 or more watery stools or > 800 grams/24 hours or requires outpatient IV hydration	ER visit or hospitalization for hypotensive shock
Headache	No interference with activity	Repeated use of non-narcotic pain reliever > 24 hours or some interference with activity	Significant; any use of narcotic pain reliever or prevents daily activity	ER visit or hospitalization
Fatigue	No interference with activity	Some interference with activity	Significant; prevents daily activity	ER visit or hospitalization
Myalgia	No interference with activity	Some interference with activity	Significant; prevents daily activity	ER visit or hospitalization

Infusion reaction	Requires no intervention and transient in duration	Requires slowing of infusion or non-prescription drug treatment	Requires prescription drug treatment presence of respiratory symptoms	ER visit or hospitalization
Illness or clinical adverse event (as defined according to applicable regulations)	No interference with activity	Some interference with activity not requiring medical intervention	Prevents daily activity and requires medical intervention	ER visit or hospitalization

Serum	Mild (Grade 1)	Moderate (Grade 2)	Severe (Grade 3)	Very Severe (Grade 4)**
Sodium – hyponatremia mEq/L or mmol/L:	132 – 134	130 – 131	125 – 129	<125
Sodium – hypernatremia mEq/L or mmol/L:	144 – 145	146 – 147	148 – 150	>150
Potassium – hyperkalemia mEq/L or mmol/L:	5.1 – 5.2	5.3 – 5.4	5.5 – 5.6	>5.6
Potassium – hypokalemia mEq/L or mmol/L:	3.5 – 3.6	3.3 – 3.4	3.1 – 3.2	<3.1
Glucose – hypoglycemia mg/dL: mmol/L:	65 – 69 3.6 – 3.8	55 – 64 3.0 – 3.5	45 – 54 2.5 – 2.9	<45 <2.5
Glucose – hyperglycemia Fasting - mg/dL: mmol/L: Random – mg/dL: mmol/L:	100 – 110 5.5 – 6.0 110 – 125 6.1 – 6.8	111 – 125 6.1 – 6.8 126 – 200 6.9 – 11.0	>125 >6.8 >200 >11.0	Insulin requirement or hyperosmolar coma
Blood urea nitrogen (BUN) – mg/dL: mmol/L:	23 – 26 8.3 – 9.5	27 – 31 9.6 – 11.2	>31 >11.2	Requires dialysis
Creatinine – elevated mg/dL: umol/L:	1.5 – 1.7 121 – 145	1.8 – 2.0 146 – 170	2.1 – 2.5 171 – 208	>2.5 or requires dialysis >208 or requires dialysis
Calcium – hypocalcemia mg/dL: mmol/L:	8.0 – 8.4 2.00 – 2.10	7.5 – 7.9 1.87 – 1.99	7.0 – 7.4 1.75 – 1.86	<7.0 <1.75
Calcium – hypercalcemia mg/dL: mmol/L:	10.5 – 11.0 2.63 – 2.76	11.1 – 11.5 2.77 – 2.88	11.6 – 12.0 2.89 – 3.00	>12.0 >3.00
Magnesium – hypomagnesemia mg/dL: mmol/L:	1.3 – 1.5 0.52 – 0.62	1.1 – 1.2 0.43 – 0.51	0.9 – 1.0 0.37 – 0.42	<0.9 <0.37
Phosphorus – hypophosphatemia mg/dL: mmol/L:	2.3 – 2.5 0.73 – 0.80	2.0 – 2.2 0.63 – 0.72	1.6 – 1.9 0.51 – 0.62	<1.6 <0.51
CPK – elevated mg/dL or ukat/L:	1.25 – 1.5 x ULN***	1.6 – 3.0 x ULN	3.1 – 10 x ULN	>10 x ULN
Albumin – hypoalbuminemia g/dL: g/L:	2.8 – 3.1 28 – 31	2.5 – 2.7 25 – 27	<2.5 <25	---- ----
Total protein – hypoproteinemia g/dL: g/L:	5.5 – 6.0 55 – 60	5.0 – 5.4 50 – 54	<5.0 <50	---- ----
Alkaline phosphatase (ALP) – increased	1.1 – 2.0 x ULN	2.1 – 3.0 x ULN	3.1 – 10 x ULN	>10 x ULN
Liver Function Tests (LFT): AST, ALT – increased	1.1 – 2.5 x ULN	2.6 – 5.0 x ULN	5.1 – 10 x ULN	>10 x ULN
Bilirubin (with any increase in LFT) - increased	1.1 – 1.25 x ULN	1.26 – 1.5 x ULN	1.51 – 1.75 x ULN	>1.75 x ULN
Bilirubin (with normal LFT) - increased	1.1 – 1.5 x ULN	1.6 – 2.0 x ULN	2.1 – 3.0 – x ULN	>3.0 x ULN

Cholesterol – increased mg/dL: mmol/L:	201 - 210 6.0 – 6.3	211 – 225 6.4 – 6.7	>226 >6.7	---- ----
Pancreatic enzymes: amylase, lipase – increased	1.1 – 1.5 x ULN	1.6 – 2.0 x ULN	2.1 – 5.0 x ULN	>5.0 x ULN

6. \*\* The clinical signs or symptoms associated with laboratory abnormalities might result in characterization of the laboratory abnormalities as Very Severe (Grade 4). For example, a low sodium value that falls within a grade 3 parameter (125-129 mEq/L) should be recorded as a Grade 4 hyponatremia event if the subject had a new seizure associated with the low sodium value.
7. \*\*\* ULN (upper limit of normal) dependent on normal reference ranges per institutional parameters.

Hematology	Mild (Grade 1)	Moderate (Grade 2)	Severe (Grade 3)	Very Severe (Grade 4)
Hemoglobin (Female) – g/dL: g/L:	11.0 – 12.0 110 – 120	9.5 – 10.9 95 – 109	8.0 – 9.4 80 – 94	<8.0 <80
Hemoglobin (Male) – g/dL: g/L:	12.5 – 13.5 125 – 135	10.5 – 12.4 105 – 124	8.5 – 10.4 85 – 104	<8.5 <85
WBC – increased cells/mm  : cells x 10  /L:	10,800 – 15,000 10.8 – 15.0	15,001 – 20,000 15.1 – 20.0	20,001 – 25,000 20.1 – 25.0	>25,000 >25.0
WBC – decreased cells/mm  : cells x 10  /L:	2,500 – 3,500 2.5 – 3.5	1,500 – 2,499 1.5 – 2.4	1,000 – 1,499 1.0 – 1.4	<1,000 <1.0
Lymphocytes – decreased cells/mm  : cells x 10  /L:	750 – 1,000 0.8 – 1.0	500 – 749 0.5 – 0.7	250 – 499 0.3 – 0.4	<250 <0.3
Neutrophils – decreased cells/mm  : cells x 10  /L:	1,500 – 2,000 1.5 – 2.0	1,000 – 1,499 1.0 – 1.4	500 – 999 0.5 – 0.9	<500 <0.5
Eosinophils – increased cells/mm  : cells x 10  /L:	650 – 1,500 0.7 – 1.4	1,501 – 5,000 1.5 – 5.0	>5,000 >5.0	Hypereosinophilic
Platelets – decreased cells/mm  : cells x 10  /L:	125,000 – 140,000 125 – 140	100,000 – 124,000 100 – 124	25,000 – 99,000 25 – 99	<25,000 <25
International normalized ratio (INR) – increased	>1.0 – 1.10 x ULN**	1.11 – 1.20 x ULN	1.21 – 1.25 x ULN	>1.25 x ULN
Partial thromboplastin time (PTT) – increased	>1.0 – 1.2 x ULN	1.21 – 1.4 x ULN	1.41 – 1.5 x ULN	>1.5 x ULN
Fibrinogen – increased mg/dL: g/L:	400 – 500 4.00 – 5.00	501 – 600 5.01 – 6.00	>600 >6.00	---- ----
Fibrinogen – decreased mg/dL: g/L:	150 - 200 1.50 – 2.00	125 – 149 1.25 – 1.49	100 - 124 1.00 – 1.24	<1.0 or associated with gross bleeding or disseminated intravascular coagulation (DIC)

8. \*\* “ULN” is the upper limit of the normal range.

Urine	Mild (Grade 1)	Moderate (Grade 2)	Severe (Grade 3)	Very Severe (Grade 4)
Protein	Trace	1+	2+	Hospitalization or dialysis
Glucose	Trace	1+	2+	Hospitalization for hyperglycemia
Blood (microscopic) – red blood cells per high power field (rbc/hpf)	1 – 10	11 – 50	>50 and/or gross blood	Hospitalization or packed red blood cells (PRBC) transfusion

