## 2.2 Design

This is a Phase 2 single site, randomized, blinded comparison of the immunogenicity, of RVi and RVa when administered RIG or SYN023. Subjects will be randomized into one of four dose regimens with a ratio of 1:1:1:1 (Table 2.2-1). The trial is planned at one site. All injections will be given intramuscularly

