### **3.2.4 Exclusion Criteria**

**Subjects must have none of the following at the time of subject ID assignment:**

1. Oral temperature  $\geq 37.5^{\circ}\text{C}$  at screening
2. Complete blood count (CBC) and platelet count abnormal values ( $>5\%$  above the upper limit of normal [ULN] or  $>5\%$  below the lower limit of normal [LLN] per local laboratory parameters) at screening with exception of absolute lymphocyte count.
3. Abnormally elevated aspartate aminotransferase (AST), alanine aminotransferase (ALT), total bilirubin, alkaline phosphatase (ALP), or creatinine (Cr) values at screening (however a single test AST, ALT or ALP may be  $>10\%$  above the ULN per local laboratory parameters)
4. Abnormal PT (INR) PTT
5. Abnormal screening urinalysis result that is, per the investigator, clinically significant, or a screening urine dipstick result of  $\geq 2+$  protein
6. Positive screening urine test for illicit drugs (opiates, cocaine, amphetamines, methamphetamines, barbiturates, benzodiazepines, tetrahydrocannabinol, PCP, MDMA, and methadone)
7. History or evidence of autoimmune disease
8. History or evidence of any past, present, or future possible immunodeficiency state, including laboratory evidence of human immunodeficiency virus (HIV) 1 or 2 infection
9. History or evidence of chronic hepatitis

10. History or evidence of rabies infection
11. History or evidence of any other acute or chronic disease that, in the opinion of the investigator, may interfere with the evaluation of the safety or immunogenicity of the drug or compromise the safety of the subject; for example a clinically relevant history of respiratory, thyroid, gastrointestinal, renal, hepatic, hematological, lymphatic, oncologic, cardiovascular, psychiatric, neurological, musculoskeletal, genitourinary, infective, inflammatory, immunological, dermatological or connective tissue disease
12. History or evidence of allergic disease or reaction, including adverse responses to therapeutic monoclonal antibodies that, in the opinion of the investigator, may compromise the safety of the subject
13. History of non-compliance that, in the opinion of the investigator, will make it unlikely that the subject will comply with the protocol
14. Previous exposure to rabies vaccine
15. Receipt of an immunoglobulin or blood product within 90 days prior to Study Day 0

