### **3.6.3.5 Clinical Assessments and Laboratory Tests**

#### **Abnormal Clinical Assessments and Laboratory Tests**

Results from clinical laboratory tests obtained on the study must be reviewed by the investigator (or a designee who is a medically qualified study team member) within 72 hours of receiving the results to determine if abnormalities exist. If the laboratory value is abnormal and has increased in toxicity grade (see Appendix E for toxicity grading scales) from baseline values, it must be reported as an adverse event and repeated promptly to demonstrate resolution. Additional laboratory tests may be performed if the investigator deems them to be necessary to fully evaluate an adverse event. In the event that the investigator elects to order non-protocol-specified laboratory tests, the investigator must record the rationale for the tests and a determination of clinical significance of the result in the source documents. The investigator must keep the medical monitor informed of adverse events of clinical significance.

Abnormal results and findings will be discussed with the subject, or the subject will be referred for follow-up with their healthcare provider if necessary.

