#### **5.1.1 Principal Investigator**

The principal investigator has a personal responsibility to closely monitor trial subjects and an inherent authority to take whatever measures necessary to ensure their safety. The principal investigator has the authority to terminate, suspend or require changes to a clinical trial for safety concerns and may delay an individual's study drug administration or pause study drug administration in the whole trial if the investigator has some suspicion that the study drug might place a subject at significant risk. The principal investigator determines severity and causality with respect to the study drug for each adverse event. For blinded studies the principal investigator is blinded, in which case the study drug may consist of a placebo, an active control, or the investigational product.

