#### **5.1.3 Medical Monitor**

The local medical monitor is the sponsor's representative and is a licensed physician or surgeon in their country of residence. The local medical monitor reviews the safety of the product for protocols in a specific region and determines expectedness of the adverse event. The local medical monitor may make a sponsor's assessment of severity and causality for adverse events that may upgrade the degree of severity and causality determined by the principal investigator. The local medical monitor, unlike the principal investigator, is unblinded for the study.

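### Minor: the creatinine row of the Toxicity Table gives mg/dL and umol/L limits that do not convert, so 2.0 mg/dL is Grade 2 in one unit and Grade 3 in the other

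*Protocol*

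**What the plan says.** The creatinine row in the serum part of Appendix E gives these limits:

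| Grade | mg/dL | umol/L |
|---|---|---|
| 1 | 1.5-1.7 | 121-145 |
| 2 | 1.8-2.0 | 146-170 |
| 3 | 2.1-2.5 | 171-208 |
| 4 | >2.5 or dialysis | >208 or dialysis |

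The Grade 3 cell is printed as "2.1 – 2.5 171 – 208". The note above the table attributes the scale to a final US regulatory guidance. It says that "laboratory values are in conventional and SI units", that the values are guidelines, and that they depend on the institution's normal parameters. Neither the note nor any other section names a governing unit.

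The grades are put to use in several places:

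- Section 3.6.3.5 requires an AE report "If the laboratory value is abnormal and has increased in toxicity grade" from baseline.
- Section 5.4 records Grade 1 as mild, Grade 2 as moderate, and Grades 3 and 4 as severe.
- Section 6.1 pauses dosing for a Grade 3 or 4 event judged at least possibly related. CPK and visually read dipstick findings are exempt; creatinine is not.
- Section 6.2 makes a Grade 3 or 4 event a stopping criterion, with the same exemptions, unless the SMC finds it unrelated to SYN023.
- Section 7.6.1 counts newly abnormal values at Grade 1 or above.

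**The concern.** Limits printed side by side in two units should give one grade for one blood sample. If they do not, the grade depends on the unit in which the laboratory happens to report, which the protocol leaves open. The edge that matters is between Grades 2 and 3, because that is where a related event begins to pause dosing.

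Creatinine is not an incidental analyte in this trial. Section 3.6.3.4 describes immune complex illness as a possible result of giving anti-rabies antibody close to vaccine, and names raised serum creatinine as a sign of the resulting glomerular damage.

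**Working it through.** **Inputs.** The limits come from Appendix E, as tabulated above. The documents give no conversion factor. I assume 10,000 / 113.12 (molar mass in g/mol) = 88.4 umol/L per mg/dL, and try 88.0 to 88.5 as a range.

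**Step 1: do the cut-points convert?** To allow for rounding, take the edge midway between adjacent printed limits, for example 2.05 mg/dL between 2.0 and 2.1, and 170.5 umol/L between 170 and 171. For Grade 3/4 take the printed 2.5 and 208.

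| Edge | mg/dL | Printed umol/L | mg/dL x 88.4 | Implied factor | Printed is low by |
|---|---|---|---|---|---|
| 0/1 | 1.45 | 120.5 | 128.2 | 83.10 | 6.0% |
| 1/2 | 1.75 | 145.5 | 154.7 | 83.14 | 5.9% |
| 2/3 | 2.05 | 170.5 | 181.2 | 83.17 | 5.9% |
| 3/4 | 2.5 | 208 | 221.0 | 83.20 | 5.9% |

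Factors of 88.0 to 88.5 give 5.5% to 6.1%. The printed umol/L column is not reproduced.

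**Step 2: could it be rounding?** Place each edge within its rounding gap so as to favour the table most. The largest implied factors are then 121/1.4 = 86.4, 146/1.7 = 85.9, 171/2.0 = 85.5 and 208/2.5 = 83.2, all below 88.0. A near-constant offset at four edges is not rounding, and the row is legible, so it is not damage to the table.

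**Step 3: the value that matters.** 2.0 x 88.4 = 176.8, which rounds to 177 umol/L. In mg/dL this is Grade 2 (1.8-2.0); in umol/L it is Grade 3 (171-208). The range of factors gives 176.0 to 177.0, with the same result.

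**Step 4: where else do the columns disagree?** Each whole umol/L value from 100 to 260 was converted, rounded to one decimal in mg/dL, and graded both ways.

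| umol/L | By mg/dL | By umol/L | Consequence |
|---|---|---|---|
| 121-128 | ungraded | Grade 1 | AE report or count, only if the value is also abnormal at the site |
| 146-154 | Grade 1 | Grade 2 | CRF mild or moderate |
| 171-181 | Grade 2 | Grade 3 | CRF moderate or severe; pausing and stopping threshold |
| 209-225 | Grade 3 | Grade 4 | none for either rule or for CRF severity |

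Among results reported to one decimal in mg/dL, the discordant ones are 1.4, 1.7, 2.0, 2.4 and 2.5. These are points on a grid, not expected frequencies; the documents give none.

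**Step 5: limits that would match.** Rounding the converted edges in Step 1 to contiguous whole numbers gives 129-154 / 155-181 / 182-221 / >221 umol/L. Every one-decimal result from 1.3 to 2.7 mg/dL then takes the same grade in both units. In whole umol/L, only 222-225 still disagree (Grade 3 versus 4), with no effect on the rules or on CRF severity.

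**The case against.** The strongest reply is that no grading step uses both columns. A result arrives in one unit and is graded in that column. Section 2.2 says "The trial is planned at one site". If the laboratory reports mg/dL, the umol/L column is never read. If it reports umol/L, every subject meets the same, lower limits, and the trial would pause sooner rather than later. This stands, and it removes any suggestion of bias between arms under consistent use of one unit.

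Other safeguards also stand:

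- Section 3.2.4 excludes abnormally elevated liver tests "or creatinine (Cr) values at screening", so few such results are expected.
- A grade-based pause needs a judgement of relatedness.
- Section 5.1.1 lets the investigator pause dosing "if the investigator has some suspicion that the study drug might place a subject at significant risk", whatever the grade.
- Under Section 5.1.3 the medical monitor's own assessment "may upgrade the degree of severity and causality determined by the principal investigator".
- Study drug is given once, on Day 0, so a pause affects later enrolment and not further study drug for the subject concerned.

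Three replies do not stand. Calling the values guidelines allows adaptation to local ranges but does not reconcile two columns. The attribution to regulatory guidance cannot be checked here and does not matter, because the protocol adopts these limits for its own rules. SAP Section 9.3 allows unit adjustment, but only when results from more than one laboratory are normalised for summaries, not for AE grading.

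A reader might extend the point to BUN and calcium, which also carry two sets of limits. Those rows convert to within 2.4% and 1.0%. What remains is immaterial rounding at the edge of Grade 1.

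**Conclusion.** The row is wrong as written, and the point is minor. The umol/L cut-points are about 6% below the mg/dL ones, assuming 88.4 umol/L per mg/dL (5.5% to 6.1% over 88.0 to 88.5), and no unit is named as governing. The consequence for the safety rules is confined to 171-181 umol/L, which includes 2.0 mg/dL.

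Three stronger readings are not supported:

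- **That a Grade 3 creatinine would by itself stop the trial.** Section 6.1 requires a relatedness judgement before a grade-based pause. Section 5.1.4 convenes the SMC when dosing is paused, so by that route the judgement comes before Section 6.2 applies.
- **That 1.4 mg/dL would change AE reports or counts.** Sections 3.6.3.5 and 7.6.1 also require the value to be abnormal, and the site's upper limit of normal is not given.
- **That study conclusions are affected.** SAP Section 9 plans no inferential analysis of safety data, and the SAP's flags and shift tables use laboratory reference ranges rather than Appendix E.

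**What to change.** - Add one sentence naming the unit that the study laboratory reports as governing for all Appendix E grading and for Sections 6.1 and 6.2. This alone settles which grade applies.
- Correct the creatinine umol/L bands to about 129-154 / 155-181 / 182-221 / >221, so that the columns agree wherever it matters.
- Before that, have the sponsor's safety physicians confirm that the mg/dL limits are the intended ones. If they are not, one-decimal mg/dL limits cannot reproduce the printed umol/L edge between Grades 2 and 3: 170/88.4 = 1.92 and 172/88.4 = 1.95 (1.946 before rounding) both report as 1.9 mg/dL, yet fall on either side of it.

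The cost is one table row, one sentence, and IRB/IEC submission and approval under Section 12. No new data are needed. Results already graded need another look only if they were graded under limits that change or in mixed units.
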